### **8.1.2 Adverse events of special interest**

Adverse events of special interest consist of AEs for which there is a specific interest in connection with pasireotide treatment (i.e. where pasireotide may influence a common mechanism of action responsible for triggering them). The adverse events of special interest may require reporting additional information and completion of the event-specific checklists and/or questionnaires.

Targeted follow-up may be required for the following: hypocortisolism/cortisol withdrawal syndrome, hyperglycemia, and QTc interval prolongation.

### **8.1.3 Laboratory test abnormalities**

#### **8.1.3.1 Definitions and reporting**

Laboratory abnormalities that constitute an Adverse event in their own right (are considered clinically significant, induce clinical signs or symptoms, require concomitant therapy or require changes in study treatment), should be recorded on the Adverse Events CRF. Whenever possible, a diagnosis, rather than a symptom should be provided (e.g. anemia instead of low hemoglobin). Laboratory abnormalities that meet the criteria for Adverse Events should be followed until they have returned to normal or an adequate explanation of the abnormality is found. When an abnormal laboratory or test result corresponds to a sign/symptom of an already reported adverse event, it is not necessary to separately record the lab/test result as an additional event.

Laboratory abnormalities, that do not meet the definition of an adverse event, should not be reported as adverse events. A Grade 3 or 4 event (severe) as per CTCAE does not automatically indicate a SAE unless it meets the definition of serious as defined below and/or as per investigator's discretion. A dose hold or medication for the lab abnormality may be required by the protocol in which case the lab abnormality would still, by definition, be an adverse event and must be reported as such.

## **8.2 Serious adverse events**

### **8.2.1 Definitions**

Serious adverse event (SAE) is defined as one of the following:

- Is fatal or life-threatening
- Results in persistent or significant disability/incapacity
- Constitutes a congenital anomaly/birth defect
- Is medically significant, i.e., defined as an event that jeopardizes the patient or may require medical or surgical intervention to prevent one of the outcomes listed above

- Requires inpatient hospitalization or prolongation of existing hospitalization
- Note that hospitalizations for the following reasons should not be reported as serious adverse events:
  - Routine treatment or monitoring of the studied indication, not associated with any deterioration in condition
  - Elective or pre-planned treatment for a pre-existing condition that is unrelated to the indication under study and has not worsened since signing the informed consent
  - Social reasons and respite care in the absence of any deterioration in the patient's general condition
- Note that treatment on an emergency outpatient basis that does not result in hospital admission and involves an event not fulfilling any of the definitions of a SAE given above is not a serious adverse event

### **8.2.2 Reporting**

To ensure patient safety, every SAE, regardless of suspected causality, occurring after the patient has provided informed consent and until 30 days after the patient has stopped study treatment must be reported to Novartis within 24 hours of learning of its occurrence. Any SAEs experienced after this 30 days period should only be reported to Novartis if the investigator suspects a causal relationship to the study treatment. Recurrent episodes, complications, or progression of the initial SAE must be reported as follow-up to the original episode within 24 hours of the investigator receiving the follow-up information. An SAE occurring at a different time interval or otherwise considered completely unrelated to a previously reported one should be reported separately as a new event.

Information about all SAEs is collected and recorded on the Serious Adverse Event Report Form. The investigator must assess and record the relationship of each SAE to each specific study treatment (if there is more than one study treatment), complete the SAE Report Form in English, and send the completed, signed form by fax within 24 hours to the Novartis Chief Medical Office and Patient Safety (CMO&PS).

Detailed instructions regarding the SAE submission process and requirements for signatures are to be found in the investigator folder provided to each site. The original copy of the SAE Report Form and the fax confirmation sheet must be kept with the case report form documentation at the study site.

Follow-up information is sent to the same contact(s) to whom the original SAE Report Form was sent, using a new SAE Report Form stating that this is a follow-up to the previously reported SAE and giving the date of the original report. Each re-occurrence, complication, or progression of the original event should be reported as a follow-up to that event regardless of when it occurs. The follow-up information should describe whether the event has resolved or continues, if and how it was treated, and whether the patient continued or withdrew from study participation.

If the SAE is not previously documented in the Investigator's Brochure or Package Insert (new occurrence) and is thought to be related to the Novartis study treatment, an oncology Novartis Chief Medical Office and Patient Safety (CMO&PS) department associate may

urgently require further information from the investigator for Health Authority reporting. Novartis may need to issue an Investigator Notification (IN), to inform all investigators involved in any study with the same drug that this SAE has been reported. Suspected Unexpected Serious Adverse Reactions (SUSARs) will be collected and reported to the competent authorities and relevant ethics committees in accordance with Directive 2001/20/EC or as per national regulatory requirements in participating countries.

### **8.3      Pregnancies**

To ensure patient safety, each pregnancy in a patient on study treatment must be reported to Novartis within 24 hours of learning of its occurrence. The pregnancy should be followed up to determine outcome, including spontaneous or voluntary termination, details of the birth, and the presence or absence of any birth defects, congenital abnormalities, or maternal and/or newborn complications.

Pregnancy should be recorded on a Clinical Study Pregnancy Form and reported by the investigator to the oncology Novartis Chief Medical Office and Patient Safety (CMO&PS) department. Pregnancy follow-up should be recorded on the same form and should include an assessment of the possible relationship to the Novartis study treatment of any pregnancy outcome. Any SAE experienced during pregnancy must be reported on the SAE Report Form.

Pregnancy outcomes should be collected for the female partners of any males who took study treatment in this study. Consent to report information regarding these pregnancy outcomes should be obtained from the mother.

[figure not shown]
A newborn of a patient (or a partner of a patient) who becomes pregnant during the study within 1 month of the last pasireotide s.c. dose, should be followed for 3 months post-delivery (from Day 0 to Month 3 of life).

### **8.4      Warnings and precautions**

No evidence available at the time of the approval of this study protocol indicated that special warnings or precautions were appropriate, other than those noted in the provided Investigator Brochure. Additional safety information collected between Investigator Brochure updates will be communicated in the form of Investigator Notifications. This information will be included in the patient informed consent and should be discussed with the patient during the study as needed.

### **8.5      Steering committee**

The steering committee will be established that will provide guidance for the analysis and the conduct of the study. It will consist of at least an independent medical expert in Cushing's disease, one study investigator and one Novartis physician. The roles and responsibilities of the Steering Committee will be defined in the Steering Committee Charter.

## 9 Data collection and management

### 9.1 Data confidentiality

Information about study subjects will be kept confidential and managed under the applicable laws and regulations. Those regulations require a signed subject authorization informing the subject of the following:

- What protected health information (PHI) will be collected from subjects in this study
- Who will have access to that information and why
- Who will use or disclose that information
- The rights of a research subject to revoke their authorization for use of their PHI.

In the event that a subject revokes authorization to collect or use PHI, the investigator, by regulation, retains the ability to use all information collected prior to the revocation of subject authorization. For subjects that have revoked authorization to collect or use PHI, attempts should be made to obtain permission to collect follow-up safety information (e.g. has the subject experienced any new or worsened AEs) at the end of their scheduled study period.

[figure not shown]
The data collection system for this study uses built-in security features to encrypt all data for transmission in both directions, preventing unauthorized access to confidential participant information. Access to the system will be controlled by a sequence of individually assigned user identification codes and passwords, made available only to authorized personnel who have completed prerequisite training.

Prior to entering key sensitive personally identifiable information (Subject Initials and exact Date of Birth), the system will prompt site to verify that this data is allowed to be collected. If the site indicates that country rules or ethics committee standards do not permit collection of these items, the system will not solicit Subject Initials. Year of birth will be solicited (in the place of exact date of birth) to establish that the subject satisfies protocol age requirements and to enable appropriate age-related normal ranges to be used in assessing laboratory test results.

### 9.2 Site monitoring

Before study initiation, at a site initiation visit or at an investigator's meeting, Novartis personnel (or designated CRO) will review the protocol and CRFs with the investigators and their staff. During the study, the field monitor will visit the site regularly to check the completeness of patient records, the accuracy of entries on the CRFs, the adherence to the protocol to Good Clinical Practice, the progress of enrollment, and to ensure that study treatment is being stored, dispensed, and accounted for according to specifications. Key study personnel must be available to assist the field monitor during these visits.

The investigator must maintain source documents for each patient in the study, consisting of case and visit notes (hospital or clinic medical records) containing demographic and medical information, laboratory data, electrocardiograms, and the results of any other tests or assessments. All information recorded on CRFs must be traceable to source documents in the patient's file. The investigator must also keep the original signed informed consent form (a signed copy is given to the patient).

The investigator must give the monitor access to all relevant source documents to confirm their consistency with the CRF entries. Novartis monitoring standards require full verification for the presence of informed consent, adherence to the inclusion/exclusion criteria and documentation of SAEs. Additional checks of the consistency of the source data with the CRFs are performed according to the study-specific monitoring plan.

### **9.3 Data collection**

The designated investigator staff will enter the data required by the protocol into the Electronic Case Report Forms (eCRF). The eCRFs have been built using fully validated secure web-enabled software that conforms to 21 CFR Part 11 requirements. Investigator site staff will not be given access to the EDC system until they have been trained. Automatic validation programs check for data discrepancies in the eCRFs and, allow modification or verification of the entered data by the investigator staff.

The Principal Investigator is responsible for assuring that the data entered into eCRF is complete, accurate, and that entry and updates are performed in a timely manner.

### **9.4 Database management and quality control**

Novartis personnel (or designated CRO) will review the data entered by investigational staff for completeness and accuracy. Electronic data queries stating the nature of the problem and requesting clarification will be created for discrepancies and missing values and sent to the investigational site via the EDC system. Designated investigator site staff are required to respond promptly to queries and to make any necessary changes to the data.

Concomitant treatments and prior medications entered into the database will be coded using the WHO Drug Reference List, which employs the Anatomical Therapeutic Chemical classification system. Medical history/current medical conditions and adverse events will be coded using the Medical dictionary for regulatory activities (MedDRA) terminology.

Samples and/or data will be processed centrally and the results will be sent electronically to Novartis (or a designated CRO).

The investigator or designee should register a patient into the IVR and IWR system when a patient is screened, enrolled and discontinued from the study treatment. The IVR and IWR system will prompt the investigator to answer a few key inclusion/exclusion. When patient is discontinued from the study treatment, the status of study completion must be registered into the IVR and IWR system.

The occurrence of any protocol violations will be determined. After these actions have been completed and the data has been verified to be complete and accurate, the database will be declared locked. Authorization is required prior to making any database changes to locked data, by joint written agreement between the Global Head of Biostatistics and Data Management and the Global Head of Clinical Development.

For EDC studies, after database lock, the investigator will receive a CD-ROM or paper copies of the patient data for archiving at the investigational site.

## **10 Statistical methods and data analysis**

This is a phase II exploratory study to assess the efficacy and safety of pasireotide s.c. alone and in combination with cabergoline in patients with Cushing's disease.

The data will be analyzed by Novartis and/or designed CRO. It is planned that the data from all centers that participate in this protocol will be used.

Two separate analyses will be made one related to the core phase and one related to the overall phase, including the core and the extension phases.

Continuous variables will be summarized by number of patients, mean, standard deviation, minimum, 25th quantile, median, 75th quantile and maximum. Categorical variables will be summarized by absolute and relative frequencies.

Unless otherwise stated, baseline assessment refers to the last assessment prior to the patient's first study drug dose recorded after the signing of the informed consent.

In addition to the statistical methods outlined, further details and any additional exploratory analyses that may be performed will be described in the Statistical Analysis Plan (SAP).

### **10.1 Analysis sets**

#### **10.1.1 Full Analysis Set**

The Full Analysis Set (FAS) comprises all patients to whom study treatment has been assigned.

#### **10.1.2 Safety Set**

The Safety Set includes all patients who received at least one dose of study medication.

#### **10.1.3 Per-Protocol Set**

The Per-Protocol Set (PPS) consists of a subset of the patients in the FAS who received at least one dose of the study drug and had no major protocol violations. The protocol deviations criteria will be defined prior to database lock.

## **10.2 Patient demographics/other baseline characteristics**

Demographic and other baseline data will be summarized descriptively for the FAS.

Categorical data will be presented as frequencies and percentages. For continuous data, mean, standard deviation, median, 25th and 75th percentiles, minimum, and maximum will be presented.

#### **10.2.1 Treatments (study treatment, concomitant therapies, compliance)**

Descriptive statistics will be used to summarize the dose intensity and duration of drug exposure. The actual and planned doses administered and reason for dose change will be listed. Concomitant medications and significant non-drug therapies prior to and after the start of the study treatment will be summarized by ATC class and preferred term.

These analyses will be performed on the safety set.

### **10.2.2 Primary objective**

To evaluate the overall efficacy of the treatment regimen of pasireotide alone or in combination with cabergoline in patients with Cushing's disease with the proportion of patients who attain mUFC  $\leq$  1.0 ULN at week 35.

#### **10.2.2.1 Statistical hypothesis, model, and method of analysis**

The trial is exploratory in nature and no formal hypothesis testing is planned.

- The proportion of patients with normalized mUFC at week 35 will be reported along with its corresponding asymptotic 95% CI.

### **10.2.3 Handling of missing values/censoring/discontinuations**

Patients missing mUFC at week 35, the last available mUFC assessment at or after week 31 will be carried forward as the week 35 mUFC assessment. However, if any patient discontinue between week 31 and week 35, then the patient's week-31 assessment will not be carried forward for week 35, and the week 35 mUFC assessment will be considered as non-response. Any patient who discontinue before week 31 will be considered as non-responder.

Sensitivity analyses may be performed using different methods for handling missing mUFC data to assess the robustness of the primary efficacy analysis. Details will be presented in the analysis plan.

### **10.2.4 Supportive analyses**

An additional analysis on the primary efficacy variable will also be performed using the PPS and the same handling of missing values as described above.

The primary efficacy endpoint at week 35 will be summarized by baseline mUFC categories.

- $1 \times \text{ULN} < \text{baseline mUFC} \leq 2.0 \times \text{ULN}$
- $2 \times \text{ULN} < \text{baseline mUFC} \leq 5.0 \times \text{ULN}$
- $5.0 \times \text{ULN}$

### **10.3 Secondary objectives**

The secondary efficacy analysis will be performed on the FAS.

**Assess the changes in mUFC from baseline to study end at each scheduled visit where UFC is measured.**

Descriptive summary statistics of actual and percentage change in mean 24h-UFC from baseline to each scheduled visit where UFC is measured will be provided along with corresponding two-sided 95% CIs.

**Assess overall efficacy of pasireotide alone or in combination with cabergoline as measured by normal mUFC levels at each scheduled visit.**

Proportion of patients with normalized mUFC (i.e. mUFC  $\leq$  1.0xULN) at each scheduled visit will be reported along with its corresponding 95% CI.

**Evaluate the overall efficacy of pasireotide alone or in combination with cabergoline as measured by controlled and partially controlled mUFC levels at each scheduled visit when mUFC is measured.**

Proportion of patients who attained mUFC  $\leq$  1.0 X ULN (controlled) or have at least 50% reduction (partially controlled) at each scheduled visit will be reported along with its corresponding 95% CI.

**Evaluate the duration of controlled or partially controlled mUFC response.**

Duration of controlled or partially controlled response is defined as the period starting from the date of patient's first normalization (mUFC  $\leq$  1.0xULN) or at least 50% reduction from baseline up to the date when the patient's mUFC  $>$  1.0xULN and the reduction from baseline falls to less than 50% for the first time. Patients without a loss of response will be censored at their last available mean UFC assessment date. The median and 95% confidence interval (CI) of duration of response will be derived from Kaplan-Meier curve and will be presented.

**Assess the effect on plasma ACTH and serum cortisol.**

Plasma ACTH and serum cortisol concentrations will be summarized using descriptive statistics at each scheduled visit. Actual and percent changes from baseline at each scheduled post baseline visit will also be presented along with 95% CIs. Mean serum cortisol and plasma ACTH results over time will be presented graphically.

**Assess the effect of continuous measures of clinical symptoms of hypercortisolism.**

Actual and percentage change from baseline in the following clinical symptoms of Cushing's disease (blood pressure, body mass index, waist circumference, fasting serum lipid profile and weight) will be assessed over time using descriptive statistics.

**Assess the effect on the categorical measures of clinical signs of hypercortisolism.**

Change in clinical signs of Cushing's disease: facial rubor, supraclavicular and dorsal fat pads, hirsutism, striae and muscle strength will be assessed using shift tables. Two assessors blinded to the visit number will score each qualitative endpoint (facial rubor, hirsutism, supraclavicular and dorsal fat pads and striae) by review of duplicated photographs. The investigator will adjudicate non-agreeing assessments. Table 10-1 below describes scales and endpoint definitions for each of these assessments. For each clinical sign, descriptive summary statistics will be presented.

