## 2.2 Rationale for the study design

This is an open-label, multi-center international non-comparative study with adult patients with confirmed diagnosis of Cushing's disease. The study will consist of patients who have never received pasireotide or patients who have received pasireotide sometimes in the past but was discontinued for reasons not related to safety. The study will also enroll pasireotide-treated patients who at the time of screening have not achieved biochemical control despite maximal tolerated doses of pasireotide for at least 8 weeks.

Pasireotide naïve patients will start pasireotide monotherapy at the dose of 0.6 mg s.c. bid. If at the end of the 8 week treatment period, the biochemical control is not achieved and the 0.6mg bid dose is well tolerated, the pasireotide dose will be increased to 0.9mg bid. If the 0.9mg bid dose of pasireotide does not lead to biochemical control, cabergoline will be added with a starting dose of 0.5mg qd. If the combination dose of 0.9mg bid of pasireotide plus 0.5mg qd cabergoline does not achieve biochemical control, the cabergoline dose will be increased to 1.0mg qd.

Patients who are currently treated with maximal tolerated doses of pasireotide monotherapy for at least 8 weeks at screening without achieving normal mUFC will enter the study with combination therapy with cabergoline. Cabergoline starting dose will be 0.5mg qd.

The stepwise approach implemented in the trial is consistent with clinical practice where patients are first started on monotherapy and, if necessary, combinations are considered.

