### 3 Objectives and endpoints

**Table 3-1 Objectives and related endpoints**

Objective	Endpoint	Analysis
Primary		Refer to Section 10.2.2
1. To evaluate the overall efficacy of the treatment regimen of pasireotide alone or in combination with cabergoline in patients with Cushing's disease	1. Proportion of patients who attain mUFC $\leq 1.0 \times \text{ULN}$ at week 35 with pasireotide alone or in combination with cabergoline	
Secondary		Refer to Section 10.3
1. To assess the changes in mUFC from baseline to study end at each scheduled visit where UFC is measured	1. Actual and percentage change in mUFC from baseline to study end at each scheduled visit when UFC is measured	
2. To assess overall efficacy of pasireotide alone or in combination with cabergoline as measured by normal mUFC levels at each scheduled visit when UFC is measured	2. Proportion of patients that attain mUFC $\leq 1.0 \times \text{ULN}$ as assessed at each scheduled visit when UFC is measured	
3. To evaluate overall efficacy of pasireotide alone or in combination with cabergoline as measured by controlled and partially controlled mUFC levels at each scheduled visit when UFC is measured	3. Proportion of patients who attain mUFC $\leq 1.0 \times \text{ULN}$ or have at least 50% reduction from baseline in mUFC as assessed at each scheduled visit when UFC is measured	
4. To evaluate the duration of controlled or partially controlled mUFC response	4. Duration of controlled or partially controlled response is defined as the period starting from the date of patient's first normalization (mUFC $\leq 1.0 \times \text{ULN}$ ) or at least 50% reduction from baseline up to the date when the patient's mUFC $> 1.0 \times \text{ULN}$ and the reduction from baseline falls to less than 50% from the first time	
5. To assess the effect on plasma ACTH and serum cortisol	5. Change from baseline in plasma ACTH and serum cortisol over time	
6. To assess the effect on the continuous measures of clinical symptoms of hypercortisolism	6. Actual and percentage change from baseline in clinical symptoms over time: blood pressure, body mass index, waist circumference, fasting serum lipid profile, and weight	
7. To assess the effect on the categorical measures of clinical signs of hypercortisolism	7. Shift from baseline in clinical signs over time: facial rubor, fat pads, hirsutism, striae (via photographs) and muscle strength	

Objective	Endpoint	Analysis

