If patient cannot increase from 0.6mg twice a day to 0.9mg twice a day due to safety, and is not yet biochemically controlled, combination with cabergoline 0.5mg qd can be initiated right away with pasireotide at 0.6mg twice a day (see [Table 6-2](#)).

If patient is being escalated to 0.9mg twice a day, but cannot tolerate the dose, dose should be reduced to 0.6mg twice a day. If the latter dose does not lead to biochemical control, combination with cabergoline as described above can be initiated (see [Table 6-2](#)).

If combination pasireotide and cabergoline 0.5mg once a day is not tolerated, the dose of cabergoline can be reduced to 0.5mg every other day. If 0.5mg every other day is not tolerated, and biochemical control is not achieved, patient should be considered for discontinuation if no clinical benefit is derived (see [Table 6-2](#)).

If combination pasireotide and cabergoline 1.0mg once a day is not tolerated, the dose of cabergoline can be reduced to 1.0mg every other day. If 1.0mg every other day is not tolerated, and biochemical control is not achieved, patient should be considered for discontinuation if no clinical benefit is derived (see [Table 6-2](#)).

The minimum treatment of any regimen is 8 weeks. Patients losing biochemical control at any time point after the 8 week period will have the dose of the study medication increased immediately to the next level provided that the dose is well tolerated.

For patients whose starting dose is 0.6mg pasireotide twice a day monotherapy, at weeks 9, 18 and 27, before patient's UFC results are available, the investigator may select one of the following two options to dispense study medication to the patient for the next 5-9 weeks of treatment:

Option 1: The investigator dispenses study medication at the current dose, plus study medication at the next dose level at the end of week 8, 13, 17, 22, 26, or 31 visits. When patient's UFC results are available, the investigator should phone the patient to inform him/her to either remain at the current dose or titrate up to the next monotherapy dose level or start the combination therapy.

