#### **7.2.1.6 Categorical measures of clinical signs of hypercortisolism**

The results of all the following assessments will be recorded in the CRF.

The following symptoms will be evaluated using photographs taken at visits in the core and extension phases as indicated in [Table 7-1](#) and [Table 7-2](#):

**Facial rubor, hirsutism, striae, and supraclavicular and dorsal fat pad.** Two photographs, one frontal and one lateral from the shoulders up will be taken to assess facial plethora, supraclavicular and dorsal fat pads. Two photographs, frontal and dorsal of the trunk with patient in standing position will be taken to assess striae, and hirsutism. The photographs must be assessed by a qualified physician at the site, who is blinded to the dose given to the patient and to the time point at which the photographs were taken. Consisting with confidentiality requirements these will not be published without explicit written permission by the patient.

For further assessment of hirsutism, the Ferriman-Gallywey score (see [Appendix 5](#)), a method of evaluating and quantifying hirsutism in women, will be used. Female patients will be asked not to shave or use any methods of hair removal during the 3 weeks prior to corresponding visits if possible.

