**Table 10-1 Categorical clinical signs**

Clinical Symptom	Scale	Tool/Endpoint
Facial Rubor(redness)	0=none, 1=mild, 2=moderate,3=severe	Photographic interpretation, Count & percent shifts from baseline
Supraclavicular and dorsal fat pads	0=none, 1=mild, 2=moderate,3=severe	Photographic interpretation, Count & percent shifts from baseline
Hirsutism	Sum area scores to total body score,	Photographic interpretation, Descriptive % change from baseline
Striae	0=none, 1=mild, 2=moderate,3=severe	Photographic interpretation, Count & percent shifts from baseline
Muscle strength	0= minimum, 3= maximum	Direct observation of ability to stand unaided. Descriptive % change from baseline

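### Disagreements between masked photograph readers go to the investigator with no masking required, and the protocol describes the reading in two different ways

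*Protocol*

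**What the plan says.** Change in clinical signs is the seventh secondary endpoint in Protocol Table 3-1: "Shift from baseline in clinical signs over time: facial rubor, fat pads, hirsutism, striae (via photographs) and muscle strength". Muscle strength is observed directly. The other signs are read from photographs.

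The reading is described in three places.

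- **Protocol 10.3, categorical clinical signs:** "Two assessors blinded to the visit number will score each qualitative endpoint". Disagreements are handled by one sentence: "The investigator will adjudicate non-agreeing assessments".
- **SAP 6.5.2, categorical clinical signs:** repeats both sentences. For scales and endpoint definitions it points to Table 2-2 of the earlier core-phase SAP.
- **Protocol 7.2.1.6:** "The photographs must be assessed by a qualified physician at the site, who is blinded to the dose given to the patient". The same sentence adds masking to the time point of the photograph. It mentions neither a second reader nor adjudication.

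Two other places show what the investigator knows. Protocol 2.2 states the design: "This is an open-label, multi-center international non-comparative study with adult patients with confirmed diagnosis of Cushing's disease". Protocol 6.4.1 says that once UFC results arrive, "the investigator should phone the patient to inform him/her to either remain at the current dose or titrate up to the next monotherapy dose level".

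Protocol Table 10-1 grades facial rubor, fat pads and striae from 0 to 3 and reports shifts. Hirsutism is handled differently: "Sum area scores to total body score", reported as percent change from baseline.

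**The concern.** With no control arm, the evidence on these signs is the change from baseline within each patient. The scores are subjective, and concealing the visit from the reader is the main protection against scoring later photographs as better because improvement is expected. The plan provides that protection for the first two scores and then requires no masking of the person who settles disagreements. Those are the readings on which two masked assessors could not agree, so they are probably the ones most open to expectation.

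At stake are the descriptive shift tables for facial rubor, fat pads and striae, and the percent change in the hirsutism score. Separately, a site that follows 7.2.1.6 literally might supply one score per photograph, while 10.3 and the SAP assume two.

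**Working it through.** The plan gives no agreement rate, kappa or precision for the photograph endpoints, so there is no figure to reproduce. The check is a comparison of texts, followed by an illustration on assumed agreement rates.

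**Step 1. The three descriptions side by side.**

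| | Protocol 7.2.1.6 | Protocol 10.3 | SAP 6.5.2 |
|---|---|---|---|
| Readers | a site physician | two | two |
| Masked to visit or time point | yes | yes | yes |
| Masked to dose | yes | not stated | not stated |
| Disagreements | not mentioned | investigator | investigator |
| Masking of adjudicator | not applicable | not stated | not stated |

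The texts differ on the number of readers, on masking to dose and on whether adjudication exists.

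**Step 2. What the adjudicator could know.** The design is open-label (2.2). The investigator receives the UFC results and tells the patient whether to change dose (6.4.1). Under 7.2.1.6, two of the photographs show the patient from the shoulders up, so a treating investigator could recognise the patient without a label. Knowledge of the regimen and the biochemical response is therefore available to the adjudicator, and no text withholds the visit.

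**Step 3. How many results could be touched.** Let *a* be the assumed chance that the two assessors give the same score to a photograph.

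- Share of reads adjudicated = 1 − *a*.
- A shift from baseline uses two reads. If these are independent, the share of shifts with at least one adjudicated read = 1 − *a*².
- Without independence, that share lies between 1 − *a* (the same patients discordant both times) and 2(1 − *a*) (never the same patients).

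| Assumed *a* | Reads adjudicated | Shifts touched, independent reads | Range without independence |
|---|---|---|---|
| 90% | 10% | 1 − 0.81 = 19% | 10–20% |
| 80% | 20% | 1 − 0.64 = 36% | 20–40% |
| 70% | 30% | 1 − 0.49 = 51% | 30–60% |
| 60% | 40% | 1 − 0.36 = 64% | 40–80% |

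These are shares of results in which an adjudicated score plays a part. They do not measure bias.

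**Step 4. Hirsutism.** Protocol Appendix 5 lists nine body areas. I assume that these are the areas summed in Table 10-1 and that areas agree independently. The chance of agreement on all nine is then 0.9⁹ = 39% at 90% agreement per area, and 0.8⁹ = 13% at 80%. If any difference in any area counts as disagreement, 61% to 87% of hirsutism reads go to the investigator. If only the totals are compared, the share is smaller, because area differences can cancel. If a tolerance is allowed, it is smaller again. The plan does not say which applies.

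**The case against.** The strongest reply is that the documents never call the adjudicator unblinded. They show an open-label trial and an investigator who handles UFC results and dosing. They do not say that visit labels are visible when a photograph is adjudicated, and an investigator who recognises a face may not know which visit it comes from. This stands: lack of masking is an inference. The point is that masking is not required.

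A reader might infer that 7.2.1.6 and 10.3 cannot both be followed. That goes too far. The wording of 7.2.1.6 can be read as setting the qualification and masking of whoever reads, and two masked site physicians plus an adjudicator would satisfy both. The texts need aligning, but they are not mutually exclusive.

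The effect may also be small. If the adjudicator must choose one of the two masked scores, the final score cannot leave the range between them. The plan does not impose that limit, but it does not rule it out either.

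Finally, the core-phase SAP cited for scales and definitions is not among the documents. It may contain masking rules, and this cannot be checked.

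**Conclusion.** The point holds in a limited form. For discordant photographs, the final score is set by someone whose position gives access to treatment and response, and no masking is required. This could bias the shift tables for rubor, fat pads and striae and the percent change in hirsutism. The reading procedure is also described inconsistently between 7.2.1.6 on one side and 10.3 and the SAP on the other.

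A reader might go further and conclude that the blinding fails, or that the tables are biased toward improvement. The documents support neither. Concordant readings keep their masking. The direction of any bias is plausible but not shown, and its size is unknown. The percentages in the working rest on assumed agreement rates.

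The consequence is confined to secondary, descriptive summaries in an exploratory trial without formal tests. The mUFC primary endpoint and the directly observed muscle strength score do not pass through this adjudication.

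**What to change.** 1. Replace investigator adjudication with a joint re-read by the same two assessors, still masked to both visit and dose. This needs a short consensus step and no additional reader.
2. The current SAP is an addendum dated after database lock, so reading may already be complete. In that case, apply a fixed rule to the two recorded scores, identically at baseline and at every later visit. For the 0–3 signs the rule should keep whole grades, for example by taking the more severe score. A mean would give half-grades that have no row or column in a shift table. The more severe score raises the recorded severity somewhat at all visits, but it does so without knowledge of visit or treatment. This option requires that both scores were kept, and it means re-resolving readings already adjudicated.
3. Define disagreement for the summed hirsutism score: by area, by total, or by total with a stated tolerance.
4. Make Protocol 7.2.1.6, Protocol 10.3 and SAP 6.5.2 state the same number of readers and the same masking.
5. Report, for each sign, how many readings were discordant, so that the reach of the rule is known.
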